9.5 Adverse Event Follow-up

AEs occurring during the course of the study must be followed until resolution or the last visit planned by the protocol. AEs not resolved by the last visit planned by the protocol will be listed in the CRF as continuing/not resolved.

Subjects who experience the onset of an AE thought to be related to IMP after their final visit (Visit 12 or the end of study visit) will be followed up until the resolution of the AE or for 30 days after the AE occurs, whichever comes first. AEs not resolved after 30 days will be listed in the CRF as continuing/not resolved. SAEs thought to be related to IMP occurring after the final visit (Visit 12 or the end of study visit) must be reported as described in [Section 10.3](#).

9.6 Pregnancy

If a female subject or the partner of a male subject believes she is pregnant (e.g., missed period, self-administered pregnancy test) the subject will be instructed to return to the clinical unit within 48 hours to undergo a serum pregnancy test. All confirmed pregnancies that occur within this study will be followed until resolution (i.e., termination [voluntary or spontaneous] or birth).

If the pregnancy is confirmed before the subject receives IMP, the subject will be excluded from study participation and will not receive IMP.

Pregnancy (without associated unexpected or adverse sequelae) is not a reportable AE but must be reported to the Sponsor within 24 hours of the Investigator or study staff first becoming aware of the subject's condition.

10 SERIOUS ADVERSE EVENTS

10.1 Definition of Serious Adverse Event

A SAE is any AE that meets any of the following criteria:

- Results in Death.
- Is Life-threatening.
- Requires Inpatient hospitalization or prolongation of existing hospitalization.
- Results in Persistent or significant disability/incapacity.
- Is a Congenital anomaly/birth defect in the offspring of a subject who received IMP.

Other important medical events that may not result in death, be life-threatening, or require hospitalization, may be considered an SAE when, based upon appropriate medical judgment, they may jeopardize the subject and may require medical or surgical intervention to prevent one of the outcomes listed in this definition. Examples of such events are:

- Intensive treatment in an emergency room or at home for allergic bronchospasm.
- Blood dyscrasias.
- Convulsions that do not result in inpatient hospitalization.

10.2 Definition of Terms

Life threatening: An AE is life threatening if the subject was at immediate risk of death from the event as it occurred; i.e., it does not include a reaction that if it had occurred in a more serious form might have caused death. For example, drug induced hepatitis that resolved without evidence of hepatic failure would not be considered life threatening even though drug induced hepatitis can be fatal.

Hospitalization: AEs requiring hospitalization should be considered SAEs. Hospitalization for elective surgery for a pre-existing condition that has not worsened or hospitalization for routine clinical procedures that are not the result of an AE need not be considered AEs or SAEs. If anything untoward is reported during the procedure, that occurrence must be reported as an AE, either 'serious' or 'non-serious' according to the usual criteria.

In general, hospitalization signifies that the subject has been detained (usually involving at least an overnight stay) at the hospital or emergency ward for observation and/or treatment that would not have been appropriate in the physician's office or outpatient setting. When in doubt as to whether 'hospitalization' occurred or was necessary, the AE should be considered serious.

Disability/incapacitating: An AE is incapacitating or disabling if the experience results in a substantial and/or permanent disruption of the subject's ability to carry out normal life functions.

10.3 Reporting Serious Adverse Events

Any SAE occurring during the course of a study, i.e. between signature of the ICF and the end-of-study visit, irrespective of the treatment received by the subject MUST be reported to the Sponsor or their representative. The Investigator must complete and fax a "Serious Adverse Event Form" to the Sponsor or their designee within 24 HOURS of occurrence or knowledge of the event.

An Investigator's delegate may complete the SAE form; however, the Principal Investigator or delegate physician must sign it. The form can be sent to the Sponsor or their designee with the delegate's signature if the Principal Investigator/delegate physician's signature cannot be obtained within one working day. The Principal Investigator/delegate physician's signature must be obtained as soon as possible, as must his/her evaluation of the relationship to the IMP. The signed form must be faxed to the Sponsor or their designee immediately.

The SAE form must be completed in English.

10.3.1 Follow-up

If follow-up information is not available at the time of the event, this information must be forwarded to the Sponsor or their designee within one day of knowledge. The Sponsor or their designee may request information as needed.

10.3.2 Post-Study Serious Adverse Events

Any SAE occurring after the end of study visit and that is considered by the Investigator to be possibly or probably related to the IMP must be reported to the Sponsor or their designee as described above.

If the end of study visit is performed less than 28 days after IVT injection, ALL SAEs occurring between the end of study visit until 28 days after IVT injection will be reported to the Sponsor or their designee, regardless of their relationship to the IMP.

10.3.3 Notification to Regulatory Authorities/Gene Therapy Bodies/IRBs/IECs

The Sponsor or their designee is responsible for notifying serious and unexpected AEs to Health Authorities and to IRBs/IECs in accordance with local law.

Gene Therapy Bodies will be informed as locally required.

10.3.4 Information to Investigator

When an SAE has been reported to Health Authorities, the Sponsor or their designee will inform all other Investigators working in this study as well as those working with GS010 in other studies in accordance with local laws and regulations.

10.3.5 *Documentation*

All SAEs will be reported on the AE pages of the CRF using the same information as documented on the SAE form and in source documents. Copies of SAE forms will be filed in the Investigator Site File along with copies of any correspondence with the IRB/IEC. The Investigator Site File will also include copies of notification letters and/or faxes of forms sent to Health Authorities and Gene Therapy Bodies if appropriate.

11 QUALITY CONTROL AND ASSURANCE

11.1 Quality Control

Steps to be taken to ensure the accuracy and reliability of data include the selection of qualified Investigators and appropriate study centers, review of protocol procedures with the Investigators and associated personnel before the study, and periodic monitoring visits by the Sponsor or their designee. Written instructions will be provided for study drug preparation and dosing, and collection, preparation, and shipment of blood samples. Guidelines for CRF completion will be provided and reviewed with study personnel before the start of the study. The Sponsor (or designee) will review CRFs for accuracy and completeness during on-site monitoring visits and after transmission to the Sponsor (or designee). Any discrepancies will be resolved with the Investigator or suitably qualified designee, as appropriate.

11.2 Quality Assurance

This study will be organized, performed, and reported in compliance with the protocol, standard operating procedures (SOPs), working practice documents, and applicable regulations and guidelines.

In accordance with the standards defined in Sponsor SOPs and applicable regulatory requirements, clinical studies sponsored by the Sponsor are subject to Sponsor Quality Audits at the study sites, which will be conducted by personnel from an appropriate unit. Site visit audits will be made periodically by the Sponsor's (or the CRO's) qualified compliance auditing team, which is an independent function from the study conduct team. Audits will include, but are not limited to, review of drug supply, presence of required documents, the informed consent process, and comparison of CRFs with source documents. The Investigator agrees to participate with audits conducted at a reasonable time in a reasonable manner. Full consultation with the Investigator will be made prior to and during such an audit, which will be conducted according to the Quality Assurance Unit SOPs. In addition, this study is subject to audit by regulatory authorities. If such a regulatory inspection occurs, the Investigator agrees to allow the regulatory inspector direct access to all relevant study documents. The Investigator should contact the Sponsor immediately if this occurs and must fully cooperate with the inspection conducted at a reasonable time in a reasonable manner.

12 STATISTICS

12.1 General Considerations

A statistical analysis plan (SAP) will be prepared after the protocol is approved and before database lock occurs. The SAP will provide further details regarding the endpoints, data handling rules, and the statistical methodology to be used to address all study objectives. The SAP will also include formats for the summary and analysis tables, listings, and graphical displays.

GS-LHON-CLIN-03B (REVERSE) will include subjects affected for 181 to \leq 365 days. Evidence indicates that improvement due to gene transfer therapy may be greatest at earlier stages of disease. This trial randomizes the right eye of each subject to receive GS010 or sham treatment in a 1:1 ratio and also uses the Efron's minimization method to balance as best as possible the treatment allocation to better- and worse-seeing eyes, as described in [Section 8.6](#) for secondary analysis.

Data for quantitative variables will be presented by arithmetic mean (for other continuous variables), standard deviation (SD) median, first quartile (Q1), third quartile (Q3), minimum and maximum. Data for binary variables (responder analysis) will be presented by using counts and percentages. Least square (LS) means, 95% confidence interval and P-values will be reported derived from models and statistical tests.

12.2 Sample Size

Sample size calculation is based on the primary endpoint (LogMAR) and on the paired comparison of treated and sham eye. There is no published data regarding the within subject variance and the sample size calculation through paired comparison will therefore be very speculative for two reasons. The first reason is the within subject correlation between right and left eye and the second reason is the absence of information on the within and between subject variance of the LogMAR. Usually the within subject correlation is positive and the use of a null correlation is conservative. The absence of information on the LogMAR requires a second rough approximation of the mean and variance of LogMAR because the mean of ETDRS (Lam et al. 2014) is highly correlated to the variance of ETDRS ($R^2 = 0.839$ for the log-log relationship). This correlation is in favor of the use of the LogMAR to stabilize the variance but the transformation from ETDRS mean and variance to LogMAR mean and variance requires additional assumptions. Starting with a mean 23.4 and a standard deviation of 28.3 (Lam et al. 2014) and a difference of 20 letters on average between treated and sham eye, using the relationship between the log mean and the log variance obtained with Lam et al. (2014) results (log variance = 1.743 log mean + 0.48, $R^2 = 0.839$) and assuming a perfect lognormal distribution of ETDRS, the difference in means of the lognormal distributions is 0.65 (3.32 - 2.67) and the pooled standard deviation of the log distributions is 0.914. Assuming no correlation between both eyes, the within subject standard deviation is $(2 \times 0.914^2)^{0.5} = 1.29$. The standardized difference in means is therefore $0.65/1.29 = 0.504$ rounded to 0.50. The sample size required to get a power of 85% is exactly 36 subjects.

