7.3.1 Visual Acuity

Enrolled subjects will include those able to read letters on the ETDRS chart (“on-chart” subjects) and those unable to read letters on the ETDRS chart but able to count fingers of the examiner at a given distance (“off-chart” subjects). On-chart subjects will have visual acuity measured with the ETDRS chart and an ETDRS score will be calculated. On-chart subjects will also have a Snellen acuity obtainable from the number of lines read on the ETDRS chart.

Off-chart subjects included in the study must maintain the visual ability to allow them to count fingers of the examiner as per the selection criteria. Off-chart subjects will not have an ETDRS score or a Snellen acuity obtainable from the ETDRS chart. Snellen acuity will be obtained utilizing the measured distance at which the subject was able to count the fingers of the examiner and a standardized formula available at ([Karanjia 2014](#)):

<http://www.countfingers.com/>

The Snellen acuities of on-chart and off-chart subjects will be converted to LogMAR for statistical analysis. Snellen acuities will be transformed to LogMAR using the standard formula available at:

<http://www.myvisiontest.com/logmar.php>

Additionally, 1 ETDRS line is considered equivalent to 0.1 LogMAR.

The visual testing at Visit 4 will be conducted for safety purposes and will not be analyzed as efficacy data (see [Section 7.6.3](#)).

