## ETDRS/LogMAR and on-chart and off-chart:

- I. 1 ETDRS line = 5 letters
- II. 1 ETDRS line = 0.1 LogMAR
- III. 0.1 LogMAR = 5 ETDRS letters
- IV. 15 ETDRS letters = 0.3 LogMAR

V. A less positive/more negative LogMAR is an improvement of vision

VI. An increase in the number of ETDRS letters read is an improvement of vision

On-Chart subjects: defined as being able to read at least 3 ETDRS letters on a single line on the ETDRS chart at either 4 or 1 meters

- a. Have an obtainable Snellen equivalent obtained directly from ETDRS chart
- b. Each Snellen equivalent is assigned a LogMAR value

Off-chart Subjects: defined as a subject who cannot read at least 3 ETDRS letters on a single line of the ETDRS chart at either 4 or 1 meters and thus have no Snellen equivalent obtainable from ETDRS chart

- c. These subjects are categorized as able to either count fingers (CF), detect hand motion (HM), detect light perception (LP) or are no-light perception (NLP)
- d. For those categorized as either CF or HM a method for deriving LogMAR visual acuity is pre-specified
- e. The distance at which CF/HM vision was obtained is recorded per the standard operating procedure
- f. Study database derives the LogMAR based on this distance and the finger/hand dimensions of the examiner, per pre-specified method.

[figure not shown]

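### The sample size is labelled LogMAR but computed on ln(ETDRS letters), so the 85% is not a power for the analysed endpoint, and no stated power describes the FDA best-eye primary at 0.3 LogMAR

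*Protocol*

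**What the plan says.** Protocol 12.2 opens: "Sample size calculation is based on the primary endpoint (LogMAR) and on the paired comparison of treated and sham eye". SAP 3.3 repeats the section. It starts from a mean of 23.4 and an SD of 28.3 ETDRS letters, with a 20-letter difference between eyes. A log-log mean-variance relation and a lognormal assumption then give the inputs: "assuming a perfect lognormal distribution of ETDRS, the difference in means of the lognormal distributions is 0.65 (3.32 - 2.67"), with pooled SD 0.914. At zero between-eye correlation the SD of the difference is 1.29, the standardised difference is 0.50, and "The sample size required to get a power of 85% is exactly 36 subjects".

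The section calls the calculation very speculative and cites "the absence of information on the within and between subject variance of the LogMAR". On the choice of scale it says "This correlation is in favor of the use of the LogMAR to stabilize the variance"; Protocol 12.4.1 gives the same rationale. On correlation: "Usually the within subject correlation is positive and the use of a null correlation is conservative".

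Two statements bear on the scale. SAP 5.4 fixes "0.1 LogMAR = 5 ETDRS letters". Protocol 7.3.1 says "Off-chart subjects will not have an ETDRS score or a Snellen acuity obtainable from the ETDRS chart".

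The documents hold two other power figures:

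- SAP 3.3 adds a calculation in LogMAR: 84% at 0.3 LogMAR with 36 subjects. It uses 0.594, the Phase I/II SD of the between-eye difference in change.
- Protocol 12.4.1 gives 80% at about 30 letters for the better-eye and worse-eye ANCOVAs. These were then a follow-up, run only if an interaction test gave P below 0.15. No SD or group size is stated.

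SAP 9.5.1 makes best-GS010 against best-sham, a between-subject ANCOVA on LogMAR change, the FDA primary at alpha 0.05. SAP 3.3 gives no figure for it.

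**The concern.** A power figure has meaning only on the scale that will be tested. If 0.65 were a LogMAR difference it would be 32.5 letters (0.65 × 50), not the 20 stated. For on-chart eyes LogMAR is a straight-line rescaling of letters, and such a rescaling cannot remove a mean-variance relation. The variance-stabilising argument belongs to ln(letters), not to LogMAR.

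The practical stake is the FDA primary. The 84% uses the SD of a within-subject difference, so it says nothing direct about two groups of different people. The 30-letter figure is not stated in LogMAR, and it addresses twice the 0.3 LogMAR that the SAP calls clinically reliable. If the best-eye test is not significant, the plan does not let a reader say whether the trial was likely to detect 0.3. Protocol Appendix V allows no SAP amendment once the code is broken, so the statement must be put right before then.

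**Working it through.** All power figures use the noncentral t at two-sided 0.05. The alpha and the two-sided alternative come from SAP 9.5.1; the sample-size sections state neither.

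**1. The plan's 36.** n = ((1.960 + 1.036)/0.50)² = 35.9, so 36. This is the normal approximation; the noncentral t gives 83.1% at n = 36. The stated figure reproduces.

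**2. The scale of 0.65 and 0.914.** Read the relation in base 10: log10 v = 1.743 log10 m + 0.48. Lognormal moments are s² = ln(1 + v/m²) and μ = ln m − s²/2.

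| Mean letters | SD from relation | s² | μ |
|---|---|---|---|
| 23.4 | 27.1 | 0.851 | 2.73 |
| 43.4 | 46.5 | 0.764 | 3.39 |

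The difference is 0.66 and the pooled SD is √((0.851 + 0.764)/2) = 0.90. Anchoring the first SD on 28.3 gives 0.66 and 0.925. Both are close to the stated 0.65 and 0.914, so the inputs are ln(letters). Reading the relation in natural logs gives an SD of 0.71, which does not fit.

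**3. The paired comparison on the linear scale, n = 36.** 20 letters = 20 × 0.02 = 0.40 LogMAR.

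- SD 28.3 letters (0.566 LogMAR) in both eyes, correlation 0: d = 20/(28.3 × √2) = 0.50, power 83%.
- The plan's mean-variance relation, correlation 0: SD of the difference √(27.1² + 46.5²) = 53.8 letters, d = 20/53.8 = 0.372, power 58%.
- The SAP's SD of 0.594: d = 0.40/0.594 = 0.673, power 97.5%.

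The SAP's own calculation, d = 0.3/0.594 = 0.505, gives 83.8% and so reproduces the 84%.

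**4. The 30-letter figure.** On ln(letters), means 23.4 and 53.4 differ by 0.883. With SD 0.914 and 18 v 18, d = 0.966 and power is 80.4%. On the linear scale 30 letters is 0.6 LogMAR. Power is then 87% with SD 28.3 letters in both groups. With the mean-variance relation the SDs are 27.1 and 55.7, pooled 43.8, so d = 30/43.8 = 0.685 and power is about 51%.

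**5. The FDA best-eye primary at 0.3 LogMAR.** An 18 v 18 split is assumed from the planned balancing of 36 subjects. 80% power needs d = 0.961, so the residual SD may be at most 0.3/0.961 = 0.31. This limit needs no assumption about correlation or baseline.

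The documents give no per-eye SD of LogMAR change. Assuming equal SDs in the two eyes, SD = 0.594/√(2(1 − ρ)), with ρ the between-eye correlation of change. The residual SD is SD × √(1 − R²), with R² the share of variance explained by baseline. The ranges of ρ and R² are assumptions.

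| ρ | Per-eye SD | Power, R² = 0 | Power, R² = 0.5 | Detectable at 80%, R² = 0 | Detectable at 80%, R² = 0.5 |
|---|---|---|---|---|---|
| 0 | 0.420 | 55% | 84% | 0.40 (20 letters) | 0.29 (14 letters) |
| 0.25 | 0.485 | 44% | 72% | 0.47 (23 letters) | 0.33 (17 letters) |
| 0.5 | 0.594 | 31% | 55% | 0.57 (29 letters) | 0.40 (20 letters) |

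Using 0.566 LogMAR instead (28.3 letters, apparently the SD of a score rather than of change) gives 34% at 0.3. A 14 v 22 split lowers the tabled powers by about 1 to 2 points.

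Zero correlation, which Protocol 12.2 calls conservative for the paired calculation, is the favourable end of this table.

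**The case against.** The protocol does not hide the weakness. It calls the calculation very speculative and a rough approximation, and says that moving from letters to LogMAR needs further assumptions. With SD 28.3 letters in both eyes, the linear scale returns d = 0.50 and N = 36 again. The 0.3 LogMAR target is set in the paired paragraph of SAP 3.3, so applying it between subjects is an extension. SAP 9.5.1 will also report the adjusted best-eye difference with its 95% interval, which shows after the fact whether 0.3 is excluded.

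Much of this stands. The disclosure is real, but it concedes uncertainty about LogMAR moments without saying that 0.65 and 0.914 are not LogMAR moments. The agreement at N = 36 needs equal SDs in the two eyes, whereas the plan's own relation makes the variance rise with the mean and gives 58%. The interval will inform interpretation, but it does not replace a prior statement of what the comparison could detect.

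Three stronger readings are tempting, and the documents do not support them:

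- A reader might infer that 36 subjects are too few for the paired primary. The SAP's LogMAR calculation reproduces and supports N = 36.
- A reader might infer that the best-eye comparison has no power figure at all. Protocol 12.4.1 gives one for that comparison, although not as a primary and not in LogMAR. Its origin in ln(letters) is inferred from the 80.4% match; the section states no inputs.
- A reader might take 31% to 55% as the actual power of the FDA primary. Those figures rest on an assumed correlation and no gain from baseline adjustment.

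**Conclusion.** The concern holds as a mislabelled power calculation, and its practical weight falls on the FDA primary. The 85% is computed on ln(letters), so it is not a power for LogMAR change. For the same 20 letters on the linear scale, the documents' own inputs give anything from 58% to 97.5%, depending on the SD used. The paired analysis does not depend on the 85%, because the 84% at 0.3 LogMAR stands on its own.

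Neither that 84% nor the 30-letter figure describes the best-eye primary at 0.3 LogMAR. The firm statement is that 80% power with 18 v 18 requires a residual SD of 0.31 or less. The plan could match the paired 84% only if baseline explained about half the variance at zero correlation, and more if the correlation is positive, as the protocol says it usually is. The actual power cannot be fixed from the documents. This should be fixed, but it does not threaten the design.

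**What to change.** In SAP 3.3, before unmasking:

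- Relabel the 0.65/0.914 calculation as ln(letters) and withdraw it as the basis for power.
- Rest the paired power on 84% at 0.3 LogMAR, SD 0.594, 36 subjects, and say that this applies to the paired analysis only.
- Restate the power and detectable effect of the best-eye primary in LogMAR, for 18 v 18, with the assumed per-eye SD, between-eye correlation and variance explained by baseline. Suggested core sentence: with about 18 best-seeing eyes per group, 80% power at 0.3 LogMAR requires a residual SD of at most 0.31.

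The variance-stabilisation wording in Protocol 12.2 and 12.4.1, and the 30-letter figure in 12.4.1, can be corrected if the protocol is amended for another reason. An amendment for this alone would be disproportionate.

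The cost is a paragraph and some relabelling in the SAP. N, model and test stay as they are. The downside is a less favourable stated power for the FDA primary.
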